### **9.6.2. Discontinuation of Study Enrollment Pending Sponsor Review**

In prior CASG studies of ganciclovir and valganciclovir that have enrolled 233 subjects, the only laboratory toxicity statistically associated with antiviral treatment has been neutropenia. Halting rules for this study therefore have been constructed to interrupt study enrollment if an excessive number of subjects are experiencing neutropenia. In the CASG 102 study, 63% of subjects receiving parenteral ganciclovir developed Grade 3 or Grade 4 neutropenia. In the CASG 109 study, 38% of subjects receiving oral valganciclovir developed Grade 3 or Grade 4 neutropenia. Whether this lower rate of neutropenia relates to the mode of drug delivery is not known at this time. Assuming that 75% of subjects receiving ganciclovir developed Grade 3 or 4 neutropenia and given that randomization is expected to be balanced between those in study drug and those in placebo, the stopping rule will be based on assuming that the overall event rate for all study participants (i.e., placebo and active subjects combined) is 37.5%. Therefore, study enrollment will be stopped and an ad hoc review will be performed if a significantly higher proportion (37.5%) of subjects in this study experience Grade 3 or Grade 4 neutropenia, as detailed in the following table:

X of the first Y subjects enrolled have Grade 3 or Grade 4 neutropenia, according to the table below. The stopping rules are based on the upper tail probabilities of the cumulative binomial with probability of an event set at 0.375. The cut-off numbers were determined by obtaining the largest value such that the tail probability is less than but closest to 0.05.

Number enrolled (Y)	Stop/Investigate when number with events equals this number (X)	Probability of observing X or more events assuming p=0.375	Number enrolled (Y)	Stop/Investigate when number with events equals this number (X)	Probability of observing X or more events assuming p=0.375
4	4	0.020	30	17	0.025
5	5	0.007	31	17	0.037
6	5	0.031	32	18	0.024
7	6	0.013	33	18	0.034
8	6	0.036	34	18	0.048
9	7	0.017	35	19	0.032
10	7	0.038	36	19	0.044
11	8	0.019	37	20	0.030
12	8	0.039	38	20	0.041
13	9	0.021	39	21	0.028
14	9	0.039	40	21	0.038
15	10	0.021	41	22	0.026
16	10	0.037	42	22	0.035
17	11	0.021	43	22	0.047
18	11	0.036	44	23	0.032
19	12	0.021	45	23	0.043
20	12	0.034	46	24	0.030
21	13	0.020	47	24	0.040
22	13	0.033	48	25	0.028
23	13	0.050	49	25	0.037
24	14	0.031	50	25	0.048

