### **11.2. Sample Size Considerations**

Subjects will be randomized 1:1 to valganciclovir oral solution or valganciclovir placebo. A **sample size of 54 (27 in each arm)** has 90% power to detect a worsening of hearing from 40% to 8.0% in the treatment group based on analyzing two correlated binary outcomes with correlation coefficient of 0.55 at 2.5% level of significance (using PASS 2008 program). Randomization will be stratified by age at randomization (1 through 11 months, 12 through 23 months, 24 through 35 months, and  $\geq 36$  months) and by CMV involvement (symptomatic and asymptomatic at birth) as a marker of disease severity.

Efficacy and safety analysis will be based on intent-to-treat population (ITT), defined as any child who receives at least one dose of study medication and who has complete hearing assessment data at baseline and Month 6. Children who completed the full six weeks of study medication and have hearing assessment data at baseline and Month 6 will be included in a per protocol (PP) analysis of efficacy, which will be performed as a sensitivity analysis. Since the primary endpoint requires comparison of baseline and 6 month audiology assessments, dropouts and subjects with audiology assessments that are inadequate for study comparison will be replaced.

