Timing of study visits (days, months) for collection of urine, saliva, and blood (together with safety laboratory measurements at Study Days 1, 14, 28, 42 and 70)

During the 6 week treatment period and for 4 week thereafter, study subjects will be followed every two weeks for 6 weeks. Subjects will then be seen a month after the end of the treatment period, then at 4 and 6 months after randomization.

During the 6 week treatment period and at the 1 month post treatment period, safety labs will be checked and adverse events will be assessed. The dose of study medication will be adjusted for weight change at each of these study treatment visits, hence collection of growth parameters at each of the treatment visits. Whole blood will be obtained for CMV viral load at each of these visits as well. Hearing outcomes will be assessed at baseline and 6 months. Changes in whole blood viral load measurements will be correlated with hearing outcome.

Safety Reviews and Halting Rules

Halting rules for this study therefore have been constructed to interrupt study enrollment if an excessive number of subjects are experiencing neutropenia. Assuming that 75% of subjects receiving ganciclovir developed Grade 3 or 4 neutropenia and given that randomization is expected to be balanced between those in study drug and those in placebo, the stopping rule will be based on assuming that the overall event rate for all study participants (i.e., placebo and active subjects combined) is 37.5%. Therefore, study enrollment will be stopped and an ad hoc review will be performed if a significantly higher proportion (37.5%) of subjects in this study experience Grade 3 or Grade 4 neutropenia, as detailed in the following table:

X of the first Y subjects enrolled have Grade 3 or Grade 4 neutropenia, according to the table below. The stopping rules are based on the upper tail probabilities of the cumulative binomial with probability of an event set at 0.375. The cut-off numbers were determined by obtaining the largest value such that the tail probability is less than but closest to 0.05.

| Number enrolled (Y) | Stop/Investigate when number with events equals this number (X) | Probability of observing X or more events assuming $p=0.375$ | Number enrolled (Y) | Stop/Investigate when number with events equals this number (X) | Probability of observing X or more events assuming $p=0.375$ |
|---------------------|---|--|---------------------|---|--|
| 4 | 4 | 0.020 | 30 | 17 | 0.025 |

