Upon completion of the six month follow-up period for all study subjects, or if the study is stopped early for any reason, the study will be unmasked after all enrolled study participants have completed the Month 6 follow-up assessments and the database is frozen. In an emergency situation, in which knowledge of the treatment assignment will be used to reduce/remove an immediate hazard to a volunteer, the study PI and/or a local site PI will have the ability to access the treatment assignment. In this situation (emergency unblinding) the study/local PI must explain and justify the nature of the event that resulted in the decision to immediately unblind to the DMID Medical Monitor and the Protocol Chair as soon as possible. This justification will be documented as a protocol deviation, and the IRBs and regulatory agencies will be informed as is appropriate.

Unmasking/Unblinding may also occur when the safety of a study participant is in question. In non-emergency situations, a conference call will be held to determine whether or not unmasking of an individual study subject is necessary or appropriate. The conference call will include the Protocol Chair, Protocol Statistician, DMID Medical Monitor and Clinical Project Manager.

The DSMB access to unblinded data is to be determined and will be based on the charter. Two data reports will be generated for each DSMB meeting: Open reports (with blinded information), and Closed reports (with unblinded information). The Closed Report will be prepared by the Protocol Statistician. Open reports will be distributed to and reviewed by the Sponsor (NIAID/DMID) and the CASG CU, and will be distributed to Genetech, Inc. The Closed Reports will be distributed to the Sponsor's pharmacovigilance contractor, DMID Clinical Research Operations and Management System (CROMS), via e-mail as a password protected Adobe Acrobat document. The password will be sent in a separate email. DMID CROMS then will distribute the Closed Reports only to the DSMB and maintain the reports as access restricted files.

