6.5.2 Stopping Rules

In prior CASG studies of ganciclovir and valganciclovir that have enrolled 233 subjects, the only laboratory toxicity statistically associated with antiviral treatment has been neutropenia. Halting rules for this study therefore have been constructed to interrupt study enrollment if an excessive number of subjects are experiencing neutropenia. In the CASG 102 study, 63% of subjects receiving parenteral ganciclovir developed Grade 3 or Grade 4 neutropenia.¹ In the CASG 109 study, 38% of subjects receiving oral valganciclovir developed Grade 3 or Grade 4 neutropenia.² Whether this lower rate of neutropenia relates to the mode of drug delivery is not known at this time. Assuming that 75% of subjects receiving ganciclovir developed Grade 3 or 4 neutropenia and given that randomization is expected to be balanced between those in study drug and those in placebo, the stopping rule will be based on assuming that the overall event rate for all study participants (i.e., placebo and active subjects combined) is 37.5%. Therefore, study enrollment will be stopped and an ad hoc review will be performed if a significantly higher proportion (37.5%) of subjects in this study experience Grade 3 or Grade 4 neutropenia, as detailed in the following table:

The stopping rules are based on the tail probabilities of the cumulative binomial. If the number of subjects “X” who experience Grade 3 or 4 neutropenia is greater than or equal to “m” out of “n” subjects, enrollment into the protocol will be held as described above while the DSMB decides whether study closure should occur. The stopping rules are based on the upper tail probabilities of the cumulative binomial with probability of an event set at 0.375. The cut-off numbers were determined by obtaining the largest value such that the tail probability is less than but closest to

0.05. More specifically, the following values of (m/n) apply for this Phase II protocol:

| Number enrolled (Y) | Stop/Investigate when number with events equals this number (X) | Probability of observing X or more events assuming $p=0.375$ | Number enrolled (Y) | Stop/Investigate when number with events equals this number (X) | Probability of observing X or more events assuming $p=0.375$ |
|---------------------|---|--|---------------------|---|--|
| 4 | 4 | 0.020 | 30 | 17 | 0.025 |
| 5 | 5 | 0.007 | 31 | 17 | 0.037 |
| 6 | 5 | 0.031 | 32 | 18 | 0.024 |
| 7 | 6 | 0.013 | 33 | 18 | 0.034 |
| 8 | 6 | 0.036 | 34 | 18 | 0.048 |

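### The neutropenia halting table uses a single-binomial model that does not fit the balanced two-arm design it assumes, and its behaviour depends on an implied 0% placebo rate that conflicts with the protocol's own 21%

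*Protocol*

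**What the plan says.** Protocol 9.6.2 starts from an active-arm rate: "Assuming that 75% of subjects receiving ganciclovir developed Grade 3 or 4 neutropenia". It adds that "randomization is expected to be balanced between those in study drug and those in placebo" and halves the figure. SAP 4.1 gives the result, that "the overall event rate for all study participants (i.e., placebo and active subjects combined) is 37.5" percent, and SAP 6.5.2 repeats the balance premise.

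The cut-offs then come from one distribution: "The stopping rules are based on the upper tail probabilities of the cumulative binomial with probability of an event set at 0.375". Each is chosen by "obtaining the largest value such that the tail probability is less than but closest to 0.05". The table runs from 4 to 54 children enrolled; its last row is 27 events with a printed probability of 0.041. A crossing stops enrollment and starts an ad hoc review.

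On allocation, Protocol 11.2 says "Subjects will be randomized 1:1 to valganciclovir oral solution or valganciclovir placebo". Randomization is stratified by four age groups and two CMV groups, which makes eight cells. Neither document gives a block size or algorithm.

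In the earlier trial of intravenous ganciclovir described in Protocol 2.1.2.1, Grade 3 or 4 neutropenia occurred in 9 of 43 untreated infants (21%) and in 29 of 46 treated infants (63%).

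**The concern.** The text uses balance to obtain the 37.5% and then drops it when it computes the tails. If half the children carry one risk and half another, the pooled count varies less than a single binomial with the average risk. The printed tail probabilities are then too large for the design described.

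Halving 75% also assumes no Grade 3 or 4 neutropenia on placebo, although the protocol reports 21% without treatment. A pooled count cannot distinguish a high drug rate from a high background rate, so this hidden input largely determines when the rule fires.

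Protocol 2.3.1 relies on stopping rules to limit exposure if risk proves unacceptable, and this table is the only numerical trial-level trigger. The DSMB would read its probabilities as the rule's error rates.

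**Working it through.** **1. Reproduce the table.** For each number enrolled Y, take the smallest X with P(Bin(Y, 0.375) ≥ X) < 0.05. All 51 cut-offs and all 51 probabilities match to three decimals. Y = 23 gives 0.0496, printed as 0.050; Y = 54 gives X = 27 and 0.0410.

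**2. Variance under balance.** With Y/2 children per arm and rates a (active) and b (placebo), the variance is (Y/2)[a(1−a) + b(1−b)]. This is below the single-binomial variance by Y(a−b)²/4, so any unequal pair with the same average gives a smaller variance. At Y = 54:
- Single binomial: 54 × 0.375 × 0.625 = 12.7.
- 75%/0%: 27 × 0.75 × 0.25 = 5.1.

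**3. Tail at Y = 54, X = 27, with 27 per arm.** Sum of two binomials, all pairs averaging 37.5%:

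| Active / placebo | P(27 or more) | Printed |
|---|---|---|
| 75% / 0% | 0.75^27 = 0.0004 | 0.041 |
| 63% / 12% | 0.019 | 0.041 |
| 54% / 21% | 0.032 | 0.041 |

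**4. Reachability with 0% on placebo and exact balance.** Only treated children can have events. The cut-off exceeds the number treated at every even Y up to 48: for example 12 against 10 at Y = 20, 17 against 15 at Y = 30, 21 against 20 at Y = 40, and 25 against 24 at Y = 48. At Y = 50, 52 and 54 it equals the number treated, so every treated child must have an event. At odd Y from 43 it equals (Y+1)/2, which can be reached if the extra child is on drug.

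**5. Chance of ever crossing.** This used 40,000 simulated trials per setting, with a look after every child from 4 to 54 and events known at once. The schemes are assumptions, because the documents state none. The 90% active rate is also an assumption.

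| Scheme | 75%/0% | 90%/0% | 75%/21% | 90%/21% |
|---|---|---|---|---|
| Blocks of 2 | 0.1% | 9% | 58% | 94% |
| Blocks of 4 | 0.3% | 15% | 59% | 95% |
| Blocks of 6 | 0.5% | 16% | 59% | 95% |
| Blocks of 2 in 8 strata | 5% | 32% | 62% | 95% |
| Blocks of 4 in 8 strata | 8% | 39% | 63% | 96% |
| 27:27 in random order | 10% | 41% | 63% | 96% |
| Simple randomization | 16% | 47% | 62% | 90% |

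**6. Why 21% changes so much.** With 75% and 21%, the pooled rate is (0.75 + 0.21)/2 = 48%. The expected count at Y = 54 is 27 × 0.75 + 27 × 0.21 = 25.9, close to the cut-off of 27. The single-look tail there is 0.43, and 0.91 at 90%/21%.

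**7. Active-arm alternative, at the stated 75% for illustration.** With 10 treated children 0.75^10 = 0.056, and with 11 it is 0.042, so a tail below 0.05 is impossible before 11 treated. With 27 treated the cut-off is 25: the tail is 0.021 at 75% and 0.48 at 90%.

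**The case against.** The printed column is labelled as conditional on p = 0.375 and is correct for that. It would also be exact at each look under simple 1:1 randomization, where every child independently has a 37.5% marginal risk, and the text says only that balance is expected. A masked pooled trigger is a legitimate choice. All of this stands: the fault is the choice of model, and a reader who inferred miscalculated tails would be mistaken.

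A reader might also infer that the rule almost cannot halt the trial even if nine in ten treated children are neutropenic. The documents do not support that. It needs both 0% on placebo and tight running balance; looser schemes give 32% to 47%, and a 21% placebo rate gives 90% or more.

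The 21% comes from untreated infants in a neonatal trial, while this trial enrolls children up to their fourth birthday, so it may not carry over. That is a reason to state the placebo rate assumed, but it does not support an unstated 0%.

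Other safeguards exist. The sponsor and Central Unit may interrupt dosing or entry at any time, the medical monitor and DSMB review cumulative safety data, and Protocol 6.3 sets rules for individual children. The table is not the only protection, but these routes do not correct its probabilities.

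Finally, counting only the active arm brings limited power in a trial this small, as step 7 shows.

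**Conclusion.** The concern holds for the design the text describes. The cut-offs and tail probabilities follow from a single binomial, while the 37.5% behind them follows from balanced arms at 75% and an implied 0%. On that premise the stated error probability at 54 children is about a hundred times too large (0.041 against 0.0004). The overstatement is smaller, but remains, for the other unequal pairs averaging 37.5%.

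The direction of failure is not fixed. With 0% on placebo and small unstratified blocks the rule is nearly inert at its null (0.1% to 0.5%) and crosses in only 9% to 16% of trials at 90% active. With 21% on placebo it crosses in 58% to 63% of trials at the active rate it treats as acceptable. Neither behaviour can be read from the table, which gives single-look tails and no chance of ever halting.

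The single-look results are exact given balanced arms. The cumulative results rest on the assumed schemes, immediate ascertainment and a look after every child; simulation error is about 0.3 percentage points or less.

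**What to change.** First reconcile the 0% implied in Protocol 9.6.2 with the 21% in Protocol 2.1.2.1, and state the placebo rate assumed. Then choose one of two routes.

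- **(a) Active-arm count.** The study statistician, whom Protocol 5.4.2 already leaves unmasked, counts Grade 3 or 4 neutropenia among children on valganciclovir only. Cut-offs come from the binomial tail at the reference rate that the sponsor and DSMB choose. Crossings go to the DSMB by the existing route; SAP 4.4 provides that "The Closed Report will be prepared by the Protocol Statistician". This removes the dependence on the placebo rate.
- **(b) Masked pooled count.** Keep the present trigger, but recompute each tail as the sum of two binomials with half the children in each arm and the stated placebo rate.

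Under either route, print the chance of ever halting over a range of active and placebo rates, under the allocation scheme actually used.

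The cost is one recomputed table and some wording in Protocol 9.6.2 and SAP 4.1 and 6.5.2. Route (a) moves the trigger from a masked count to the unmasked statistician and, if the reference rate stayed at 75%, could not fire before 11 treated children. Route (b) keeps the masking but remains only as good as its placebo rate.

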## **9.7. Safety Monitoring by the DMID Safety Oversight Mechanism**

### **9.7.1. Data and Safety Monitoring Board**

A Data and Safety Monitoring Board will be established by the DMID. The DSMB members will consist of persons independent of the investigators or study team with no financial, scientific or other conflict of interest with the study and will be selected by the NIH. The initial responsibility of the DSMB will be to review and make recommendations regarding the initiation of the study. A simple majority will be considered a DSMB quorum for voting and meeting purposes. Members will be able to submit data review comments electronically if they are not able to participate in a data review meeting teleconference. After the initiation of the study and during the course of the study at intervals determined by the DMID, the DSMB will:

1. Review the research protocol, template informed consent document and plans for data and safety monitoring.
2. Evaluate the progress of the study, including periodic assessments of data quality and timeliness, participant recruitment, accrual and retention, participant risk versus benefit, performance of the trial sites, and other factors that can affect study outcome.
3. Review study endpoints for differences between groups and to assess if SAEs are occurring at a rate greater than expected.
4. Consider factors external to the study when relevant information becomes available,
5. Monitor the confidentiality of the study data and the results of monitoring.

The S&DCC will provide all data, tables, unique and repeated listings, figures, descriptive statistics, and tests of significance requested by the NIH for all DSMB meetings, interim analysis plan and final analysis.

## **10. CLINICAL MONITORING**

### **10.1. Site Monitoring Plan**

Site Monitoring will be conducted to ensure that human subject protection, study procedures, laboratory procedures, study intervention administration, and data collection processes are of high quality and meet sponsor, GCP/ICH, and regulatory guidelines, and that the study is conducted in accordance with the protocol and study manuals. NIAID/ DMID, the sponsor of this study, or its designee will conduct site monitoring visits as detailed in the monitoring plan.

Site visits will be made at standard intervals in accordance with the monitoring plan. More frequent visits may be made if needed. Monitoring visits will include, but are not limited to, review of regulatory files, case report forms, informed consent forms, medical and laboratory reports, and protocol compliance. Study monitors will meet with investigators to discuss any problems and actions to be taken and document visit findings and discussions.

Every effort will be made to maintain the anonymity and confidentiality of subjects during this study. However, because of the experimental nature of this treatment, the Investigator agrees to allow representatives of the Sponsor (DMID/NIAID) as well as authorized representatives of the Food and Drug Administration or other Regulatory agencies, Genentech/Roche, or the UAB Central Unit, to inspect the facilities used in this study and to inspect, for purposes of verification, the hospital or clinic records of all subjects enrolled into this.

## **11. STATISTICAL CONSIDERATIONS**

### **11.1. Study Hypotheses**

We hypothesize that six weeks of antiviral therapy can stabilize hearing in older infants and toddlers who have developed CMV-associated hearing loss. This study is designed as a proof of principle study.

### **11.2. Sample Size Considerations**

Subjects will be randomized 1:1 to valganciclovir oral solution or valganciclovir placebo. A **sample size of 54 (27 in each arm)** has 90% power to detect a worsening of hearing from 40% to 8.0% in the treatment group based on analyzing two correlated binary outcomes with correlation coefficient of 0.55 at 2.5% level of significance (using PASS 2008 program). Randomization will be stratified by age at randomization (1 through 11 months, 12 through 23 months, 24 through 35 months, and  $\geq 36$  months) and by CMV involvement (symptomatic and asymptomatic at birth) as a marker of disease severity.

Efficacy and safety analysis will be based on intent-to-treat population (ITT), defined as any child who receives at least one dose of study medication and who has complete hearing assessment data at baseline and Month 6. Children who completed the full six weeks of study medication and have hearing assessment data at baseline and Month 6 will be included in a per protocol (PP) analysis of efficacy, which will be performed as a sensitivity analysis. Since the primary endpoint requires comparison of baseline and 6 month audiology assessments, dropouts and subjects with audiology assessments that are inadequate for study comparison will be replaced.

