#### **5.4.6. Handling of Withdrawals**

Study subjects may withdraw voluntarily from participation in the study at any time. Up to 20% (n=10) over-enrollment is allowed to replace subjects who drop-out or who have inadequate audiology assessments. Study subjects also may withdraw voluntarily from receiving the study intervention for any reason. If a study subject withdraws or is discontinued from the study at any time prior to completion of the study, the reason for this decision will be recorded on the electronic case report form (eCRF). SAEs and AEs will be followed according to guidelines in Section 9. The study subject should be encouraged to complete follow-up visits as part of the intent to treat group.

Should a study subject's therapy be discontinued prematurely, all clinical and laboratory evaluations scheduled during the next study visit will be completed on the day the study subject is discontinued. All randomized study subjects will continue to be followed as long as possible and included in the final analysis.

Since the primary endpoint requires comparison of baseline and 6 month audiology assessments, dropouts and subjects with audiology assessments that are inadequate for study comparison (Section 11.4.1) will be replaced. Characteristics of the dropouts and those with missing outcomes will be compared to determine if there is a difference between the two treatment groups. If differences are observed, this will be included in the primary outcome reporting as a limitation.

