## **11.4. Final Analysis Plan**

### **11.4.1. Primary Outcome**

Primary analysis will be based on intent-to-treat population. Categories utilized for hearing assessment of each ear for each time point are normal hearing, mild hearing loss, moderate hearing loss, and severe hearing loss. Based on the hearing assessment of each ear at Month 6 and at Baseline, change in each ear will be categorized into binary outcomes: improved + no change versus other (i.e., worsened). For example, normal in the left ear at baseline and moderate in the same ear at Month 6 will be considered as worsened. The primary outcome will be analyzed using logistic regression based on generalized estimating equations (GEE) in order to accommodate the correlation between the left and right ears of a subject in the modeling. In addition, if there are enough data available we will adjust the analyses by whether or not a subject at birth is asymptomatic or symptomatic from their congenital CMV infection. Additional analyses will be performed to adjust for age and site plus any imbalances in the demographic and clinical characteristics to determine if adding them to the model will impact the results. P-values < 0.05 will be considered significant for the primary outcomes.

A single, independent study audiologist who is masked (blinded) to treatment assignment will assess the audiology test battery for each subject and assign the classifications of normal hearing, mild hearing loss, moderate hearing loss, or severe hearing loss based upon their hearing thresholds (in decibels). The classifications will be assigned by ear (one for the left ear and one for the right ear), giving “total ear” classifications. Following this, the study audiologist will assign the “best ear” classification for the subject at that study visit; for example, if a subject had mild hearing loss in their left ear and severe hearing loss in their right ear, then the “best ear” classification will be mild hearing loss.

Primary analyses will be done on the first 54 subjects recruited. If there were subjects enrolled as replacement for dropouts or missing outcome, these added subjects will be included in the secondary analyses.

For those with missing outcome due to missing baseline and/or Month 6 audiology (including dropouts), we will exclude them from the primary analysis. However, we will perform sensitivity analysis by replacing all missing data with “worsening” outcome.”

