6.2 Analysis Populations

(ICH E3; 9.7.1, 11.4.2.5. ICH E9; 5.2)

All enrolled subjects will be included in the basic demographic and clinical summaries and analyses. Only subjects who took at least one dose of the blinded treatment and who have completed hearing assessment data at baseline and Month 6 will be included in the analyses of study outcomes that compare treatment groups based on the intention-to-treat (ITT). Safety analyses will be done on all participants enrolled in the study. Children who have completed the full six weeks

of study medication and have hearing assessment data at baseline and Month 6 will be included in a per-protocol (PP) analysis of efficacy, which will be performed as a sensitivity analysis.

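### The population labelled ITT is a complete-case set defined by Month 6 audiology, and the documents disagree on who is analysed for hearing, virology and safety

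*Protocol*

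**What the plan says.** Protocol 11.2 bases both efficacy and safety on an intent-to-treat population defined as "any child who receives at least one dose of study medication and who has complete hearing assessment data at baseline and Month 6". SAP 6.2 carries the condition over: only dosed children "who have completed hearing assessment data at baseline and Month 6 will be included in the analyses of study outcomes" that compare the treatment groups.

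Protocol 11.4.1 says of children without paired audiology that "we will exclude them from the primary analysis", then adds that "we will perform sensitivity analysis by replacing all missing data with" a worsened result. SAP 6.4 and 8.1 say the same. Protocol 11.4.1 also states: "Primary analyses will be done on the first 54 subjects recruited". Replacement children enter the secondary analyses only.

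Protocol 5.4.6 says the opposite about who is analysed: "All randomized study subjects will continue to be followed as long as possible and included in the final analysis". Protocol 7.6 repeats this for early termination. Both sections encourage children who withdraw to finish their visits as members of the intent-to-treat group.

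**The concern.** Whether a child has a usable Month 6 audiogram is decided after randomisation. Toxicity, the course of the child's hearing, or the family's view of benefit may all affect it. A set chosen on that event no longer has the protection of randomisation, and a report calling it ITT would mislead.

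The same definition is also attached to analyses that need no audiogram. The six-week log-reduction endpoints use the Day 42 specimen, taken months before the Month 6 test, and safety follow-up ends at Day 70. Two programmers following different sections could produce different denominators for virology and safety. Protocol 2.2 expects the viral-load data to be valuable even if the hearing endpoint fails, so this is not a minor point.

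**Working it through.** **1. The plan's own figure.** Inputs from Protocol 11.2: 27 children per arm, two ears each, correlation 0.55, worsening 40% against 8%, level 2.5%.

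Effective ears per arm = 27 × 2 / (1 + 0.55) = 34.84. Pooled-variance power = Φ[(0.32√n − 1.96√(2 × 0.24 × 0.76)) / √(0.40 × 0.60 + 0.08 × 0.92)].

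With n = 34.84 this is Φ[(1.889 − 1.184) / 0.56] = Φ(1.26) = 89.6%, which reproduces the stated 90% when 2.5% is read as one-sided. With 22 per arm (n = 44/1.55 = 28.39) it is Φ(0.93) = 82.4%.

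**2. The populations side by side.**

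| Analysis | Place | Who is analysed |
|---|---|---|
| Final analysis | Protocol 5.4.6, 7.6 | All randomised |
| Efficacy and safety | Protocol 11.2 | Dosed, hearing data at baseline and Month 6 |
| All treatment comparisons | SAP 6.2 | Same as Protocol 11.2 |
| Viral-load summaries | SAP 3.3 | Early dropouts kept, through average AUC and last available value |
| Virology tables | SAP 17 | At least one dose |
| Safety | SAP 6.2 | All enrolled |
| Safety | SAP 9 | At least one dose |

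The first row cannot hold together with the second and third. SAP 6.2 also conflicts with SAP 3.3 and 17 on virology. Safety has three definitions. Enrolment comes before randomisation (Protocol 5.1), so the all-enrolled version even includes children who never receive study drug.

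**3. The planned analysis of missing hearing data.** The documents give no dropout rates by arm or outcome, so the figures in steps 3 to 5 use assumed losses. Take no true effect, with 40% worsening among observed children in both arms, 2 active and 6 placebo children missing, and all missing counted as worsened.

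- Active: (25 × 0.40 + 2) / 27 = 12.0/27 = 44.4%
- Placebo: (21 × 0.40 + 6) / 27 = 14.4/27 = 53.3%

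Each missing child adds 0.60/27 = 2.2 points to its arm, so four extra placebo losses create 8.9 points of apparent benefit. With the losses reversed, the same 8.9 points count against the drug. The rule is therefore conservative in one direction only.

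**4. An arm-asymmetric bound.** Take the design rates among completers and 5 missing per arm. Count missing active children as worsened and missing placebo children as not worsened.

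- Active: (22 × 0.08 + 5) / 27 = 6.76/27 = 25.0%
- Placebo: (22 × 0.40 + 0) / 27 = 8.8/27 = 32.6%

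The planned rule would give 25.0% against (8.8 + 5)/27 = 51.1%.

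**5. What selection can do to completers.** A simulation used 4,000 trials with 27 per arm, 40% worsening in both arms, correlation 0.55 and a Wald test on child means. With nothing missing, type I error was 5.3%. The assumed missingness was 40% on active and 10% on placebo for children with a worsened ear, and 10% and 20% for the others. The completer difference was then biased by about 10 points in favour of active, and type I error was 13.9%. Exchanging the arms gave about 10 points the other way. These rates illustrate the mechanism and do not predict what will happen in this trial.

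**The case against.** The exclusion is stated openly, and the plan has safeguards. Missing is set to worsened as a sensitivity analysis. Protocol 5.4.6 compares dropouts between arms and reports any difference as a limitation. SAP 8.1 assigns severe loss to children who receive a cochlear implant, which closes one outcome-related route to missing data. Requiring one dose is a common modified-ITT choice in a blinded trial. If the active arm loses more children, the planned analysis already works against the drug.

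All of this stands, but it does not make the set ITT. It also leaves heavier placebo loss without a conservative analysis. The per-protocol analysis is narrower still.

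A reader might infer three stronger claims that the documents do not support:

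- **That children without Month 6 audiology are plainly dropped from virology.** SAP 3.3 keeps early dropouts in the viral-load summaries, and SAP 17 lists dosed children. Neither settles the matter. SAP 17 gives the hearing tables the same label, and its average-AUC tables all relate viral load to hearing. The supportable finding is a contradiction.
- **That 10/54 = 18.5% of virology data would be lost.** Ten is the replacement cap and not a forecast. Replacements enter the secondary analyses, so ten losses with ten replacements would be 10/64 = 15.6% of children. A share of children is also not a share of samples.
- **That the ITT label lowers power to 82%.** A child without a Month 6 audiogram has no observed outcome whatever the set is called. The fall comes from missing outcomes combined with the first-54 rule, which keeps replacements out of the primary analysis.

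**Conclusion.** The point holds as a wrong label joined to an internal contradiction. The ITT set in Protocol 11.2 and SAP 6.2 is a complete-case set selected after randomisation, and Protocol 5.4.6 and 7.6 contradict it. The populations for virology and safety are inconsistent, and on the literal definition a child with Day 42 virology but no Month 6 audiogram would leave the six-week comparison.

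The number of children affected cannot be derived from the documents. The 8.9-point distortion and the 25.0% against 32.6% bound rest on assumed losses of 2 and 6, and of 5 per arm. They show how sensitive a trial of 27 per arm is to a few informative losses. They do not show that the result will be biased, or that a shift of this size alone would be significant.

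**What to change.** - Rename the present set complete-case, and define ITT as all randomised children by assigned arm.
- Analyse virology endpoints on all available data and safety on all dosed children.
- Align Protocol 11.2 with SAP 3.3, 6.2, 9 and 17, and reconcile it with Protocol 5.4.6 and 7.6.
- For hearing, add the arm-asymmetric analysis (missing active worsened, missing placebo not worsened) beside the planned one, labelled as an extreme bound. Multiple imputation is optional: at 8%, a 22-child active arm has only about 22 × 0.08 = 1.8 children's worth of events to support it.

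The cost is a text amendment and a few analyses of data already being collected. The real downside is presentation. With 5 missing per arm, a 32-point difference shrinks to 7.6 points at the bound, so the report must explain that this is a limit and not an estimate. None of these changes recovers power lost to missing audiology. That depends on retention and on the first-54 rule.
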